Pneumonia	
While ICS use is a recognised risk for pneumonia in patients with COPD. A clear causal relationship between inhaled corticosteroid use and pneumonia in subjects with asthma has not been established.
 
In an 18 study integration in the FF/VI asthma program, the incidence of pneumonia (adjusted for exposure) observed with FF/VI 100/25 and FF 100 (8.5/1000 patient years and 9.6/1000 patient years, respectively) was similar to that seen with placebo (9.3/1000 patient years). A higher incidence in the FF/VI 200/25 and FF 200 arms were observed (18.3/1000 patient years and 23.6/1000 patient years, respectively). However, the 95% CIs were wide and overlapped across all treatment groups, including placebo. Few of the pneumonia events led to hospitalisation with either strength, and there were no observed differences in the incidence of serious events between the two treatment strengths. The risk of pneumonia in asthma patients is very low and is consistent with the risk of other ICS.
 
Pneumonia experience with UMEC
 
In the All Clinical Studies grouping, the incidence of on-treatment AEs in the Pneumonia and lower respiratory tract infection (LRTI) adverse events of special interest (AESI) category with UMEC 62.5 mcg (1%; 34.6/1000SY) was similar to placebo (1%; 34.8/1000SY) and lower than the incidence reported in the UMEC 125 mcg (3%; 72.6/1000SY). A higher incidence of AEs in the Pneumonia AESI category was reported for UMEC 125 mcg (2%; 37.4/1000SY) compared with UMEC 62.5 mcg (<1%; 19.8/1000SY) and
	
Exclusion criteria:
 
 
- Immune suppression (e.g., Human Immunodeficiency Virus [HIV], Lupus) or other risk factors for pneumonia (e.g., neurological disorders affecting control of the upper airway, such as Parkinson's Disease, Myasthenia Gravis).
 
- Subjects at potentially high risk (e.g., very low body mass index [BMI] or severely malnourished) will only be included at the discretion of the Investigator.
 
 
Medical history will also be taken for pneumonia in previous 12 months, including recording of any episodes resulting in hospitalisation.
 
The occurrence of pneumonia will be recorded in the eCRF.
 
Where possible a chest X-ray should be performed to confirm a diagnosis, whenever a subject has a suspected

Potential Risk of Clinical Significance	Summary of Data/Rationale for Risk	Mitigation Strategy

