8.2. Adverse Events Analyses

Adverse events analyses including the analysis of adverse events (AEs), Serious (SAEs) and other significant AEs will be based on GSK Core Data Standards. The details of the planned displays are provided in [Appendix 11: List of Data Displays](#).

All AEs will be classified using the standard GSK Medical Dictionary for Regulatory Activities (MedDRA) dictionary, and grouped by SOC and PT, unless otherwise stated. The investigator will evaluate all AEs with respect to seriousness, severity, and causality.

The tabular summary for each type of AE listed below will include the number of participants who reported at least one event, and percentage of participants who reported at least one AE (incidence) for each SOC (where applicable), each PT, and overall. By default, adverse events will be sorted by MedDRA SOCs, in descending order from the SOC with the highest total incidence (i.e., summed across all dose groups) for any adverse event within the class, to the SOC with the lowest total incidence. If the total incidence for any two or more adverse events is equal, the events will be presented in alphabetical order. Only SOCs with observed AE PTs will be presented. Repeat sort order for MedDRA PTs within each SOC.

In principle, all safety analyses will be provided by dose group and total. However, due to Japan regulatory authority requirement, AE analyses by dose at the time of onset of the AE will be prepared in final analyses of this study. Note that dose at the time of onset of the AE will be decided by allocated dose even if a given subject has incorrect study treatment in certain period (but not during all period). If a given subject has incorrect study treatment during all period, then this subject will be analysed according to the treatment which he/she received. In interim analyses, selected tables will be provided. Please refer to Section [11.11.5](#).

Each type of the following will be summarized for both approaches (i.e., by dose group and total, by dose at the time of onset of the AE)

- AE overview during treatment period
- All AEs during treatment period (by SOC and PT; by SOC and PT and maximum severity)
- Drug related AEs during treatment period (by SOC and PT; by SOC and PT and maximum severity)
- Serious AEs during treatment period (by SOC and PT)
- AEs resulting in withdrawal from study (by SOC and PT)

- AEs of Special Interest during treatment period (by SOC and PT)

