- Most Common Adverse Events during treatment period (3% or More of subjects in Any Treatment Group) (by PT)

The following AE summaries will be provided only by dose group and total.

- All AEs adjusted for exposure (per thousand person years) during treatment period (by SOC and PT)
- All AEs during follow-up period (by SOC and PT)
- Drug related AEs adjusted for exposure (per thousand person years) during treatment period (by SOC and PT)
- Drug related AEs during treatment period and follow-up period (by SOC and PT)
- All AEs for week 0-12, week 13-24, week 25-36 and week 37-52 during treatment period (by SOC and PT)
- All AEs for week 0-24, week 25-52 during treatment period (by SOC and PT)
- Serious AEs adjusted for exposure (per thousand person years) during treatment period (by SOC and PT)
- AEs of Special Interest adjusted for exposure (per thousand person years) during treatment period (by SOC and PT)
- Common Non-Serious AEs by SOC and PT during treatment period (Number of Subjects and Occurrences) (5% or More of subjects in Any Treatment Group)
- Summary of Serious Adverse Events by System Organ Class and Preferred Term during treatment period (Number of Participants and Occurrences)
- Major Adverse Cardiac Events
- Serious Drug Related Adverse Events during treatment period (for PLS, final analysis only)
- Non-Serious Drug Related Adverse Events during treatment period (for PLS, final analysis only)

The following AE listings will be provided. These listing include information of dose group, not dose at AE.

- All AEs, Fatal serious AEs, Non-Fatal AEs, AEs leading to permanent discontinuation of study treatment or withdrawal from study
- Relationship of AE SOCs, PTs and Verbatim text
- Reasons for considering as a serious AE

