8.3. Adverse Events of Special Interest Analyses

A comprehensive list of MedDRA terms based on clinical review will be used to identify each type of event. The details of the planned displays are provided in [Appendix 11: List of Data Displays](#).

Adverse Events of Special Interest (AESI) are those AEs associated with the known pharmacological action of ICSs and/or LAMAs and/or LABAs, regardless of whether the AE has been specifically described for FF and/or UMEC and/or VI. AESI groupings are compiled in one of two ways: where SMQs (pre-defined lists of MedDRA PTs) are available from MedDRA for specific AESIs, these are used; and where SMQs are not available, a GSK-defined list of all relevant MedDRA PTs is used.

For FF/UMEC/VI, the special interest groups are: adrenal suppression, corticosteroid-associated and antimuscarinic-associated ocular effects, decreased bone mineral density and associated fractures, hypersensitivity, pneumonia, LRTI excluding pneumonia, local steroid effects, effects on potassium, tremor, CV effects, effects on glucose, asthma/bronchospasm, anticholinergic syndrome. Gastrointestinal obstruction, urinary retention.

[Table 1](#) presents the special interest AE groups for FF, UMEC and VI.

Table 1 AESI definitions

Special Interest AE Group	Special Interest AE Subgroup	PTs for Inclusion
Cardiovascular effects*	Cardiac arrhythmia	Cardiac arrhythmia (SMQ), excluding congenital and neonatal arrhythmias (SMQ)
	Cardiac failure	Cardiac Failure (SMQ)
	Cardiac ischaemia	Ischaemic Heart Disease (SMQ)
	Stroke	Central nervous system haemorrhages and cerebrovascular conditions (SMQ)
	Hypertension	Hypertension (SMQ)
Pneumonia*	Pneumonia	Infective Pneumonia (Narrow SMQ)
LRTI excluding infective pneumonia SMQ*	LRTI excluding infective pneumonia SMQ	Selected PTs

Special Interest AE Group	Special Interest AE Subgroup	PTs for Inclusion
Decreased bone mineral density and associated fractures	Decreased bone mineral density and associated fractures	Osteoporosis/Osteopenia (SMQ) Selected PTs
Hypersensitivity*	Hypersensitivity	Hypersensitivity (SMQ) Angioedema (SMQ) Anaphylactic reaction (SMQ)
Anticholinergic Syndrome*	Anticholinergic syndrome	Anticholinergic Syndrome (SMQ)
Gastrointestinal obstruction*	Gastrointestinal obstruction	Gastrointestinal obstruction (SMQ)
Adrenal Suppression	Adrenal Suppression	Selected PTs
Antimuscarinic ocular effects* / Corticosteroid Associated Eye Disorders	Glaucoma (antimuscarinic / corticosteroid)	Glaucoma (SMQ)

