	Cataracts (corticosteroids)	Lens disorders (SMQ)
Effects on Glucose	Effects on Glucose	Hyperglycaemia/new onset diabetes mellitus (SMQ)
Local steroid effects	Local steroid effects	Selected PTs
Urinary retention*	Urinary retention	Selected PTs
Effects on potassium	Effects on potassium	Selected PTs
Tremor	Tremor	Selected PTs
Asthma/Bronchospasm for Asthma-related intubations and deaths	Asthma/Bronchospasm for Asthma-related intubations and deaths	Asthma/bronchospasm (SMQ)
Dry mouth / Drying airway secretions*	Dry mouth / Drying airway secretions	Selected PTs (narrow & broad focus)

*: of interest for UMEC .

Adverse events of special interest will be summarized in the same manner outlined in Section 8.2 for overall AEs.

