12.17.	ITT	AE3	Summary of Most Common Adverse Events (3% or more of Subjects in Any Treatment Group) During Treatment Period by dose at AE (dose: FF/UMEC/VI 200/62.5/25)	ICH E3	SAC [1]
12.18.	ITT	Study Specific	Summary of Adverse Events for week 0-12, week 13-24, week 25-36 and week 37-52 During Treatment Period by dose group		SAC [1]
12.19.	ITT	Study Specific	Summary of Adverse Events for week 0-24, week 25-52 During Treatment Period by dose group		SAC [1]
12.20.	ITT	AE15	Summary of Common (>=5%) Non-serious Adverse Events by System Organ Class and Preferred Term During Treatment Period (Number of Participant and Occurrences)	FDAAA, EudraCT 'Common' to be defined by study/project team. For studies with very few events/participants, listing is sufficient: discuss this option with your disclosure representative.	SAC [1]
12.21.	ITT	AE3	Summary of Non-Serious Drug-Related Adverse Events During Treatment Period by dose group	PLS	SAC [1]
12.22.	ITT	AE1	Summary of All Drug-Related Adverse Events During Treatment Period and Follow-Up Period by dose group		SAC [1]

CONFIDENTIAL

207236

Safety: Tables					
No.	Population	IDSL / Example Shell	Title	Programming Notes	Deliverable [Priority]
Serious and Other Significant Adverse Events					
12.23.	ITT	AE1	Summary of Serious Adverse Events During Treatment Period by dose group		SAC [1]
12.24.	ITT	AE1	Summary of Serious Adverse Events During Treatment Period by dose at AE (dose: FF/UMEC/VI 100/62.5/25)		SAC [1]
12.25.	ITT	AE1	Summary of Serious Adverse Events During Treatment Period by dose at AE (dose: FF/UMEC/VI 200/62.5/25)		SAC [1]
12.26.	ITT	Study Specific	Summary of Serious Adverse Events During Treatment Period per Thousand Person-Year by dose group		IA [1]
12.27.	ITT	AE1	Summary of Adverse Events Leading to Withdrawal from Study During Treatment Period by dose group		SAC [1]
12.28.	ITT	AE1	Summary of Adverse Events Leading to Withdrawal from Study During Treatment Period by dose at AE (dose: FF/UMEC/VI 100/62.5/25)		SAC [1]
12.29.	ITT	AE1	Summary of Adverse Events Leading to Withdrawal from Study During Treatment Period by dose at AE (dose: FF/UMEC/VI 200/62.5/25)		SAC [1]
12.30.	ITT	AE1	Summary of Adverse Events of Special Interest During Treatment Period by dose group		SAC [1]
12.31.	ITT	AE1	Summary of Adverse Events of Special Interest During Treatment Period by dose at AE (dose: FF/UMEC/VI 100/62.5/25)		SAC [1]

CONFIDENTIAL

207236

Safety: Tables					

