No.	Population	IDSL / Example Shell	Title	Programming Notes	Deliverable [Priority]
12.32.	ITT	AE1	Summary of Adverse Events of Special Interest During Treatment Period by dose at AE (dose: FF/UMEC/V1 200/62.5/25)		SAC [1]
12.33.	ITT	Study Specific	Summary of Adverse Events of Special Interest During Treatment Period per Thousand Person-Year by dose group		IA [1]
12.34.	ITT	AE16	Summary of Serious Adverse Events by System Organ Class and Preferred Term during treatment period (Number of Participants and Occurrences)	FDAAA, EudraCT For studies with few events/participants listing is sufficient: discuss this option with your disclosure representative.	SAC [1]
12.35.	ITT	AE3	Summary of Serious Drug-Related Adverse Events by dose group	PLS	SAC [1]
MACE					
12.36.	ITT	Study Specific	Summary of Major Cardiac Events (MACE) – Narrow Definition		SAC [1]
12.37.	ITT	Study Specific	Summary of Major Cardiac Events (MACE) – Broad Definition		SAC [1]
Laboratory: Chemistry					
12.38.	ITT	LB1	Summary of Chemistry Data		SAC [1]
12.39.	ITT	LB1	Summary of Chemistry Changes from Baseline	ICH E3 Includes Baseline values. Includes pre-specified parameters repeated in conventional units.	SAC [1]
12.40.	ITT	LB3	Summary of Chemistry Shifts from Baseline Relative to Normal Range		SAC [1]

CONFIDENTIAL

207236

Safety: Tables					
No.	Population	IDSL / Example Shell	Title	Programming Notes	Deliverable [Priority]
Laboratory: Hematology					
12.41.	ITT	LB1	Summary of Hematology Data		SAC [1]
12.42.	ITT	LB1	Summary of Hematology Changes from Baseline	ICH E3 Includes baseline values.	SAC [1]
12.43.	ITT	LB3	Summary of Hematology Shifts from Baseline Relative to Normal Range		SAC [1]
Laboratory: Urinalysis					
12.44.	ITT	UR1	Summary of Worst Case Urinalysis Results (Discrete or Character Values) Post-Baseline Relative to Baseline	ICH E3 As above for Chemistry, using dipstick categories. Define change categories according to actual values expected from lab dataset	SAC [1]
Vital Signs					
12.45.	ITT	VS1	Summary of Vital Signs	ICH E3 Includes Baseline values.	SAC [1]
12.46.	ITT	VS1	Summary of Change from Baseline in Vital Signs	ICH E3 Includes Baseline values.	SAC [1]
ECG					
12.47.	ITT	EG2	Summary of ECG Values	IDSL	SAC [1]
12.48.	ITT	EG2	Summary of Change from Baseline in ECG Values	IDSL	SAC [1]
12.49.	ITT	Study Specific	Summary of Categories for QTc (F) Values (Interim)	IDSL	SAC [1]

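### AESI tables are specified by SOC and PT only: beyond pneumonia and the MACE composites no group in SAP Table 1 has a specified n (%), and no group has a specified rate

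*SAP*

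**What the plan says.** - **Groups.** SAP Section 8.3 says its Table 1 "presents the special interest AE groups for FF, UMEC and VI". The table has 16 groups. Cardiovascular effects has five subgroups, and the ocular group has two. Each group is built from standardised MedDRA queries, selected preferred terms, or both.
- **Incidence table.** SAP Section 8.2 lists "AEs of Special Interest during treatment period (by SOC and PT") among the tables to be produced both by dose group and by dose at onset.
- **Rate table.** The same section lists "AEs of Special Interest adjusted for exposure (per thousand person years) during treatment period (by SOC and PT"), by dose group and total.
- **Row content.** Section 8.2 asks for the number and "percentage of participants who reported at least one AE (incidence) for each SOC (where applicable), each PT, and overall". It names no AESI group row.
- **Cross-reference.** Section 8.3, where an exception would belong, closes with "Adverse events of special interest will be summarized in the same manner outlined in Section 8.2 for overall AEs".
- **Display list.** In Appendix 11, Tables 2.14 and 12.30-12.32 use shell AE1, the shell of the all-AE tables (2.3, 12.3-12.5). Tables 2.15 and 12.33 use a study-specific shell that is not shown. Titles such as "Summary of Adverse Events of Special Interest During Treatment Period by dose group" and "Summary of Adverse Events of Special Interest During Treatment Period per Thousand Person-Year by dose group" mention neither group nor subgroup.
- **Protocol.** Section 10.3.2 promises summary statistics for AESIs under the primary endpoint but does not state the level. In Section 3.3.1 the risk table reports that the incidence of events in the combined Pneumonia and LRTI "adverse events of special interest (AESI) category with UMEC 62.5 mcg (1%; 34.6/1000SY) was similar to placebo".

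**The concern.** An AESI group exists to pool preferred terms that point to one class effect of an ICS, LAMA or LABA. The natural question is how many participants had at least one event in the group, and at what rate. A table restricted to AESI terms but laid out by SOC and PT answers that for each term, for each SOC and for any AESI at all, but not for the group. With 110 participants, most PT rows will hold very few people. A modest cluster of related terms is then easy to overlook, and the reader must assemble it unaided.

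**Working it through.** The plan has no stated figure to reproduce here. The check sets the layout against the group definitions and asks what can be recovered.

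**1. Which group-level displays are specified?**

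| Display | Group-level content |
|---|---|
| 2.14, 12.30-12.32 (AESI incidence) | None specified: SOC, PT, overall |
| 2.15, 12.33 (AESI rate) | None specified: SOC and PT |
| 2.34, 12.53 (pneumonia, with chest X-ray) | Pneumonia; no rate specified |
| 2.17-2.18, 12.36-12.37 (MACE) | Ischaemia (or MI terms) and stroke as one composite; no rate specified |
| Listings 22, 65 (AESI); 16, 59 (subject numbers per AE) | Participant-level data, no summary |

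**2. Can n (%) per group be rebuilt from PT rows?** If a group's PTs have participant counts n1, n2, ..., the number of distinct participants G satisfies

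max(ni) ≤ G ≤ sum(ni),

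because one participant may appear under several PTs. As an illustration, take three PTs with 2, 1 and 1 participants and the planned N = 110 (Protocol Section 10.1):

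- PT rows: 2/110 = 1.8%, 1/110 = 0.9%, 1/110 = 0.9%
- Lower bound for the group: 2/110 = 1.8%
- Upper bound for the group: 4/110 = 3.6%

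The SOC row settles the matter only if all the group's observed PTs fall in one SOC and no other group's terms share that row. The documents do not show the SOC assignments, so this cannot be relied on.

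**3. Can the rate per group be rebuilt?** SAP Section 11.6.3 defines the rate as events × 1000 / exposure. This counts events, so PT rates add within a group. Assumed exposure is 100 completers × 1 year + 10 dropouts × 0.5 year = 105 person-years (range 100 to 110 for dropouts contributing 0 to 1 year). With one event per participant and PT in the illustration:

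2 × 1000/105 + 1 × 1000/105 + 1 × 1000/105 = 19.0 + 9.5 + 9.5, and directly 4 × 1000/105 = 38.1 per 1000 person-years.

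This needs the PT-to-group map. Table 1 gives only a reference to selected PTs for seven groups: LRTI, adrenal suppression, local steroid effects, urinary retention, potassium, tremor and dry mouth. Protocol Section 9.2.8 says the contributing terms will be documented in advance in the analysis plan.

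**4. How small are the counts?** Expected events = person-years × rate / 1000, applying each rate in Protocol Section 3.3.1 to the whole study:

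| Rate quoted | Per 1000 | Expected at 105 PY (100 to 110) |
|---|---|---|
| Pneumonia, FF/VI 100/25 | 8.5 | 0.9 (0.9 to 0.9) |
| Pneumonia, FF/VI 200/25 | 18.3 | 1.9 (1.8 to 2.0) |
| Pneumonia AESI, UMEC 62.5 mcg | 19.8 | 2.1 (2.0 to 2.2) |
| Pneumonia and LRTI AESI, UMEC 62.5 mcg | 34.6 | 3.6 (3.5 to 3.8) |

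So a whole category may hold about one to four events. Grouping does not make it precise: 2 events in 105 person-years give 19.0 per 1000, exact 95% CI 2.3 to 68.8. It does avoid dividing these few events further.

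**The case against.** The strongest reply is that this is layout, not lost information. Several parts of it stand.

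- **Some grouped displays exist.** Pneumonia has its own table, and ischaemia and stroke enter the MACE tables. A reader might infer that the trial yields no group-level figure at all; the display list does not support that.
- **The figures can be derived.** Event-based rates add across PTs given the map, and with 110 participants group counts can be taken by hand from the AESI listings.
- **A SOC row is also planned.** A reader might infer that five participants with five different arrhythmia terms would show only as five rows of 1/110. If those terms share a SOC, the SOC row shows them together, possibly mixed with other groups.
- **No benchmark is planned.** A reader might take the protocol's category rates as the yardstick for this trial. Protocol Section 3.3.1 gives them as background risk data, and no comparison with them is planned. The documents also do not say whether those rates count events or participants, so even a grouped row might not match them.
- **No protocol commitment is broken.** Protocol Section 10.3.2 does not fix the level of the AESI summary.
- **The shells are not shown.** A group layout inside AE1 or a study-specific shell cannot be excluded. It would, however, go against the explicit instruction in Section 8.2, so the text would still need correcting.

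What the reply does not meet is the absence of a specified n (%) for the remaining groups and of a specified rate for any group. Hand derivation from listings is a poor substitute for a planned table.

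**Conclusion.** The point holds as a gap in descriptive reporting. Sections 8.2 and 8.3 specify the AESI incidence and rate tables by SOC and PT only. Of the 16 groups in Table 1, only pneumonia has a table of its own; two cardiovascular subgroups appear within the MACE composites. No group or subgroup has a specified rate. In the illustration, the reader of the tables could not tell a group incidence of 1.8% from one of 3.6%.

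The illustration assumes 110 treated participants and the PT counts shown; the rates and expected counts assume about 105 person-years (100 to 110). The study has no hypotheses (SAP Section 2.4), so sample size and inference are untouched. The change is still worth making, because AESIs are part of the primary safety reporting and the groups are already defined.

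**What to change.** In SAP Sections 8.2 and 8.3, replace the SOC-and-PT layout for AESIs with rows by AESI group, subgroup and PT:

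- for n (%), count each participant once at each level;
- for the exposure-adjusted tables, give events per 1000 person-years at each level;
- apply this to Tables 2.14-2.15 and 12.30-12.33, and say so in the titles or programming notes;
- amend the closing cross-reference in Section 8.3 so that it no longer brings back the all-AE layout.

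The rows depend on the list of contributing PTs, so the SAP should contain or cite it for the groups now defined only by selected PTs. The cost is SAP wording and table programming. No new data, assessments or participants are needed.

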#### 10.3.2. Safety Analyses

All safety analyses will be performed on the ITT Population.

Endpoint	Statistical Analysis Methods
Primary	
The primary endpoint is incidence and type of AEs/SAEs. This endpoint will be summarized using the following two approaches:
 
 
1. Summary statistics will be provided for the integration of the groups and for each group separately (only FF/UMEC/VI 100/62.5/25 mcg, only FF/UMEC/VI 200/62.5/25 mcg and switching medication from FF/UMEC/VI 100/62.5/25 mcg to FF/UMEC/VI 200/62.5/25 mcg).
 
2. Summary statistics will be provided by the dose received at the time of experiencing the AE. (FF/UMEC/VI 100/62.5/25 mcg and FF/UMEC/VI 200/62.5/25 mcg)
 
 
The number and proportion of subjects experiencing at least one AE will be calculated and presented by system organ class (SOC) and by preferred term (PT). Summary statistics will also be presented for all AEs, treatment-related AEs, SAEs, AEs leading to treatment or study discontinuation, and AESI.

Secondary	
Secondary endpoints will be summarized using the approach described in approach 1 above (i.e., provided for only FF/UMEC/VI 100/62.5/25 mcg, only FF/UMEC/VI 200/62.5/25 mcg and switching medication from FF/UMEC/VI 100/62.5/25 mcg to FF/UMEC/VI 200/62.5/25 mcg).
 
Specific details will be provided in the Reporting and Analysis Plan (RAP).

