5. CONSIDERATIONS FOR DATA ANALYSES AND DATA HANDLING CONVENTIONS

5.1. Study Treatment & Sub-group Display Descriptors

5.1.1. Interim Analyses

In interim analyses, only data until 24 weeks after first treatment will be used. This means the data after switching medication will NOT be included. Therefore, description in data displays will be the same as description in RandAll NG.

Treatment Group Descriptions for Interim Analyses			
RandAll NG		Data Displays for Reporting	
Code	Description	Description	Order [1]
A	FF/UMEC/VI 100/62.5/25	FF/UMEC/VI 100/62.5/25	1
B	FF/UMEC/VI 200/62.5/25	FF/UMEC/VI 200/62.5/25	2

NOTES:

1. Order represents treatments being presented in TFL, as appropriate.

Treatment comparisons will not be displayed.

If a given subject has incorrect study treatment during all period, then this subject will be analysed according to the treatment which he/she received. However, since it is uncertain whether a given subject has incorrect study treatment during all period (for 52 weeks) as of the timing of interim analyses, all analysis will be according to the allocated dose for interim analyses.

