5.1.2.1. Analyses by dose group

In principle, description in data displays will follow the patterns taking the treatment switching into account. All final analyses will use these descriptions below, except for summaries for “AE analyses by dose at the time of onset of the AE”. This approach is based on both the allocated doses and status of treatment switch at Week 24. Note that the participants will be allocated to either FF/UMEC/VI 100/62.5/25 mcg or FF/UMEC/VI 200/62.5/25 mcg, and only the participants who are allocated to FF/UMEC/VI 100/62.5/25 mcg will be allowed to switch treatment to FF/UMEC/VI 200/62.5/25 mcg only at Week 24. Therefore, treatment descriptions will be three as below table.

In this approach, summaries for total (overall) will be also presented.

Treatment Group Descriptions for Final Analyses by dose group				
RandAll NG		Switched treatment at Week 24	Data Displays for Reporting	
Code	Description	Description	Description	Order [1]
A	FF/UMEC/VI 100/62.5/25	No (FF/UMEC/VI 100/62.5/25 after week 24 or discontinued this study by week 24)	Only FF/UMEC/VI 100/62.5/25	1
A	FF/UMEC/VI 100/62.5/25	Yes (Switched to FF/UMEC/VI 200/62.5/25 at week 24)	FF/UMEC/VI 100/62.5/25 to FF/UMEC/VI 200/62.5/25	2
B	FF/UMEC/VI 200/62.5/25	N/A (Switched treatment will not be acceptable)	Only FF/UMEC/VI 200/62.5/25	3

NOTES:

1. Order represents treatments being presented in TFL, as appropriate.

5.1.2.2. Analyses by dose the time of onset of the AE (by dose at AE)

“AE analyses by dose at the time of onset of the AE” will be planned in this study due to Japan regulatory authority requirement. In these analyses, the following descriptions will be used.

Treatment Group Descriptions for Final Analyses by dose at AE			
Dose at AE		Data Displays for Reporting	
	Description	Description	Order [1]
A	FF/UMEC/VI 100/62.5/25	FF/UMEC/VI 100/62.5/25	1
B	FF/UMEC/VI 200/62.5/25	FF/UMEC/VI 200/62.5/25	2

NOTES:

1. Order represents treatments being presented in TFL, as appropriate.

In “by dose at AE” approach, the following rule will be applied.

- If a given subject is allocated to FF/UMEC/VI 100/62.5/25 at visit 2 and not switched at visit 5 then this subject will be handled as FF/UMEC/VI 100/62.5/25.
- If a given subject is allocated to FF/UMEC/VI 200/62.5/25 at visit 2 then this subject will be handled as FF/UMEC/VI 200/62.5/25.

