8.1. Extent of Exposure

Overall extent of exposure to study treatment will be summarized in increments of 4 weeks for ≥ 1 day, ≥ 4 weeks, ≥ 8 weeks, ≥ 12 weeks, ≥ 16 weeks, ≥ 20 weeks, ≥ 24 weeks, ≥ 28 weeks, ≥ 32 weeks, ≥ 36 weeks, ≥ 40 weeks, ≥ 44 weeks, ≥ 48 weeks, ≥ 52 weeks, in addition to providing summary statistics and total treatment exposure (person-year).

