11.6.3. Safety

Adverse Events
Adverse Event Rate
Event rate per thousand person-years will be displayed for AE data in separate tables as listed in Section 11.11.5 and Section 11.11.6. Event rate per thousand person-years will be calculated as the number of events x 1000 divided by the total participant exposure during the time-period of interest (i.e., during treatment period).
AE'S OF Special Interest
Adverse events of special interest have been defined as AEs which have specified areas of interest. These consist in groupings of preferred terms based on the MedDRA dictionary version used in each reporting effort. Subgroups may be defined, based on relevant combination of preferred terms, or on Standardized MedDRA queries (SMQ).

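### Final adverse-event tables by dose at onset and by period give percentages over unequal exposure, and no planned final rate pools all person-time at each strength or is given by period

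*SAP*

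**What the plan says.** Protocol 10.3.2 sets two approaches for the primary endpoint. The first summarises AEs by dose group: 100 only, 200 only, switched from 100 to 200, and all combined. For the second, "Summary statistics will be provided by the dose received at the time of experiencing the AE".

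SAP 8.2 defines the AE tables by the number of participants with an event and the "percentage of participants who reported at least one AE (incidence) for each SOC (where applicable), each PT, and overall". It then gives two lists. The first is produced under both approaches and has no exposure-adjusted item. The second opens with "The following AE summaries will be provided only by dose group and total". It holds the four summaries per 1000 person-years (all, drug-related, serious and special-interest AEs) and the two by-period summaries.

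Other sections bear on this:

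- SAP 11.6.3 defines the rate as events times 1000, "divided by the total participant exposure during the time-period of interest (i.e., during treatment period").
- SAP 5.1.2.1 sets the three dose groups: "All final analyses will use these descriptions below, except for summaries for" AEs by dose at onset. The Only-100 group is Group 1 participants with "FF/UMEC/VI 100/62.5/25 after week 24 or discontinued this study by week 24".
- SAP 8.1 tabulates exposure in 4-week steps, "in addition to providing summary statistics and total treatment exposure (person-year").
- SAP 5.1.1 says of the interim analysis: "This means the data after switching medication will NOT be included".
- SAP 11.3.2.2 and 11.3.2.3 give the day boundaries of the period windows and cut a switcher's time at Visit 5.

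**The concern.** A percentage with at least one event rises with time observed. Where two columns rest on different lengths of observation, part of any difference between them is length alone. That holds here for the dose-at-onset tables and for the period tables.

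The final rates by dose group do not fill the gap. The switch group's rate mixes both strengths. The Only-100 rate leaves out the first 24 weeks of everyone who later switches, and the protocol permits a switch only when ACQ-7 at Week 24 exceeds 0.75, so the omitted time is not a random part. The interim rates are by allocated strength but stop before the switch.

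What is at stake is how descriptive tables for the primary endpoint are read. A flat event rate could look like a late rise, and equal rates at the two strengths could look different.

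**Working it through.** The plan states no figure for this point, so the check starts from its table list and day boundaries.

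**1. Where the final outputs sit (SAP 8.2 and 11.11.6).**

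| Output | Final tables | Split | Rate? |
|---|---|---|---|
| AEs by dose at onset | 12.4-5, 12.9-10, 12.12-13, 12.16-17, 12.24-25, 12.28-29, 12.31-32 | Strength | No; shells AE1, AE5A, AE3 |
| AEs by period | 12.18, 12.19 | Dose group and period | None in title; study-specific shell |
| AEs per 1000 person-years | 12.7, 12.14, 12.26, 12.33 | Dose group and total | Yes, whole treatment period |

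**2. Window lengths (SAP 11.3.2.2), last day minus first day plus 1.**

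- Days 1-84, 85-168 and 169-252: 84 days each. Days 253-365: 113 days, or more if Visit 7 is later. 113/84 = 1.35.
- Days 1-168: 168 days. Days 169-365: 197 days or more. 197/168 = 1.17.
- A switcher with Visit 5 on Day 169 gives 168 days at 100 and 197 at 200. The -5/+2 day visit window (Days 164-171) moves this to 163-170 and 202-195.

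**3. Effect of window length.** Assume a constant rate and no dropout. Percentage with at least one event = 1 - exp(-rate × days/365).

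| Assumed rate | 84 days | 113 days | 168 days | 197 days |
|---|---|---|---|---|
| 1 per year | 20.6% | 26.6% | 36.9% | 41.7% |
| 0.1 per year | 2.28% | 3.05% | 4.50% | 5.25% |

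No allocation or switching assumption is needed. For scale, the 6.1-point gap (26.63 - 20.56) compares with a sampling standard error of √[(0.2056×0.7944 + 0.2663×0.7337)/110] = 5.7 points, treating the windows as independent.

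**4. Effect on the dose-at-onset tables.** Here G1 is the size of Group 1, G2 = 110 - G1, and s is the share of Group 1 that switches. SAP 2.3 sets no target allocation ratio and neither document gives s, so both are assumed. Also assumed: the same rate of 1 per year at both strengths, no dropout, and everyone who received a strength counted in its denominator.

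- 100 column = (1-s)×inc(365) + s×inc(168)
- 200 column = [G2×inc(365) + s×G1×inc(197)] / (G2 + s×G1)

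| G1/G2 | s | 100 column | 200 column | 200 minus 100 |
|---|---|---|---|---|
| any | 0% | 63.2% | 63.2% | 0 |
| 55/55 | 10% | 60.58% | 61.26% | +0.7 |
| 55/55 | 50% | 50.05% | 56.04% | +6.0 |
| 80/30 | 10% | 60.58% | 58.69% | -1.9 |
| 80/30 | 50% | 50.05% | 50.92% | +0.9 |
| 30/80 | 10% | 60.58% | 62.43% | +1.9 |
| 30/80 | 50% | 50.05% | 59.82% | +9.8 |

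Both size and sign depend on the assumed shares. The +6.0 case has a sampling standard error of about 8.7 points.

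**5. Person-time the single-strength groups leave out.**

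- Share of all time at 100 missing from Only 100 = s×168 / [(1-s)×365 + s×168]: 4.9% at s = 10%, 31.5% at s = 50%.
- Share of all time at 200 missing from Only 200 = s×G1×197 / (G2×365 + s×G1×197): 5.1% and 21.3% at 55/55; 12.6% and 41.8% at 80/30.

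**The case against.** The strongest reply is that the plan does what the protocol asks. Protocol 10.3.2 calls for number and proportion, and the SAP supplies them. Protocol 5.4 plans no group comparison and no test, and SAP 5.1.2.2 says comparisons will not be shown. The period columns carry their week labels, and three of the four are equal. At 0.1 events per year the period gaps are under 0.8 points, less than one participant in 110. Dose and switching follow prior therapy and control status, and rates do not remove that selection. All of this stands, and it keeps the point small.

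Several stronger readings are tempting but not supported:

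- *That rates by strength cannot be rebuilt.* Table 12.1 should give the switch group's person-years, and each switcher's time at 100 is close to 168 days. Table 12.19 breaks that group's columns at Visit 5. Listings 47, 56 and 58 cover treatment, exposure and AEs by participant. An approximate rate could be pieced together, but none is planned.
- *That numbers at risk by period are missing.* The counts with at least 12, 24 and 36 weeks of exposure (SAP 8.1) roughly supply them.
- *That the percentages lack defined denominators.* The text does not state them, but the shells are not shown, so no defect can be claimed.
- *That the tables will favour one strength.* The sign is undetermined.
- *That the SAP departs from the protocol.* It does not.

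**Conclusion.** The point holds as a modest reporting improvement. The final dose-at-onset tables use percentages over unequal exposure. So do the period tables, with the caveat that this rests on the general rule in SAP 8.2 and on titles, because Tables 12.18 and 12.19 have study-specific shells. No planned final rate pools all person-time at each strength or is given by period.

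The unequal windows follow directly from SAP 11.3.2.2. Their effect is about 5 to 6 points at an assumed constant rate of one event per year and under 1 point at a tenth of that. The size and direction of any dose artefact remain unknown, because they turn on allocation and switching shares that the documents do not give. No test, planned comparison or stated figure changes.

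**What to change.** In SAP 8.2, 11.6.3 and 11.11.6:

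- Add person-years and rates per 1000 person-years by dose at onset for all, drug-related, serious and special-interest AEs, splitting switchers' events and time at Visit 5 as 11.3.2.3 already does.
- Add person-years and rate to Tables 12.18 and 12.19, and extend the rate definition in 11.6.3 to cover time at a strength and time in a window.
- Keep the crude percentages, and add a note that rates remove the unequal-length artefact but not selection into dose or into switching.

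The dates are already collected, so no new data are needed. The cost is SAP wording and more output: four AE types by two strengths is about eight extra tables by system organ class and preferred term, or the equivalent columns, plus columns in the two period tables.
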